Sing For Your Saunter – Dementia Supplement

NCT04518917

NIH R61AT010753-02S1

March 15, 2024

Study Design

This study was a single center, cross-sectional, interventional study.

Participants

Participants were recruited through the Movement Disorders Clinic (MDC) at Washington University in St. Louis School of Medicine. Inclusion criteria for this study were as follows: a diagnosis of idiopathic, typical Parkinson disease according to the UK Brain Bank Criteria; Hoehn & Yahr stage 2-3 (mild to moderate disease severity); stable on all PD medications for at least two months prior to study entry; normal or corrected to normal hearing; score of ≥ 1 on the Movement Disorders Society Unified Parkinson Disease Rating Scale – Part III – Motor Aspects (MDS-UPDRS-III) item #10 indicating observable gait impairment; able to walk for ten continuous minutes independently; a score of one or less on item #7 on the New Freezing of Gait Questionnaire (nFOG-Q), indicating freezing episodes are not moderately or significantly disturbing to daily walking; and dementia as defined by a Clinical Dementia Rating (CDR) score of 0.5-1.0 (very mild to mild dementia). Seventeen individuals met these inclusion criteria and were enrolled in the study.

As this was a within-group cross-over study, there was no control group and no group randomization. This study was approved by the Institutional Review Board (IRB) of Washington University in St. Louis School of Medicine.

Protocol

This study consisted of one in-person lab visit. All testing was done with participants in their on-state for medication. During the lab visit, participants were first assessed using the MDS-UPDRS-III and nFOG-Q to confirm eligibility for the study. Participants were also asked if they had any previous musical training. After eligibility was confirmed, participants were fitted with six APDM Opal sensors worn on the feet, wrists, lumbar spine, and sternum. These sensors sample at a frequency of 128 Hz and were used to collect various gait parameters, with a focus on velocity, cadence, and stride length. For all gait tasks, participants completed three

30-second trials of each cueing type and condition in a 100-foot hallway. All participants were followed by a trained physical therapist during walking trials to reduce fall risk during the intervention. No falls or adverse events occurred during data collection.

All participants first completed three 30-second uncued walking trials to determine baseline gait parameters. The average cadence over these uncued trials was then used to calculate four cueing tempos for each participant: 90%, 100%, 110%, and 120% of uncued walking cadence. These cues were selected based upon previous work in our group looking at internal vs. external cues in people with PD without dementia. Cues were rounded to the nearest five beats per minute. While cueing tempos were being calculated, participants were presented with a list of songs to choose from for the cued walking tasks. The list included songs selected with the help of a music therapist that have a 4/4 beat, salient tempo, and are likely to be familiar to many individuals. The songs available were as follows: "I've Been Working on the Railroad", "You Are My Sunshine", "This Land is Your Land", "Skip to My Lou", "She'll Be Coming Around the Mountain", "Don't Sit Under the Apple Tree", "When the Saints Go Marching In", "You Can't Hurry Love", "When Johnny Comes Marching Home Again", and "Seventy-Six Trombones." Participants were provided with the song lyrics prior to starting the cued tasks to ensure they knew the words. After reviewing the lyrics, participants were recorded singing the song out loud without reading the lyrics from the sheet to ensure they remembered the lyrics correctly. Additionally, they practiced walking and singing out loud to ensure they were able to perform the two tasks simultaneously.

After cueing tempos were determined, participants received two different cueing methods at each tempo. The two cueing methods were A) Music and B) Mental. Music served as the externally generated cue, while Mental served as the internally generated cue. For all cued trials, one chorus of the selected song was played at the correct tempo while the participant was standing still as a reminder of the tempo. Cues were delivered via speakers and volume was adjusted so participants could hear throughout the entire trial. During the Music

task, the cue kept playing and participants were instructed to walk to the beat, rather than the melody, of the song as they listened. During the Mental task, the cue turned off and participants were instructed to walk to the beat of the song while singing in their heads in silence. To ensure participants were doing the task, they were asked if they were singing in their heads after each trial. Participants were instructed not to move their mouths during the mental singing task, and this was monitored by the physical therapist who was walking with the participant for safety. Prior to the start of the cued trials, a member of the research team demonstrated walking on the beat to ensure all participants received the same instruction. To mitigate order effects, task order for each participant was randomized first by tempo, then Music vs Mental condition order was randomized within each tempo. This meant that both cueing types at a given tempo occurred one after the other, but the order of cue type presented at each tempo was random. In total, participants completed 27 walking trials of 30 seconds each.

Statistical Analysis

All data were analyzed using R statistical software. Gait parameters including velocity and stride length were averaged across the three trials for a given condition (i.e., Mental 110%). Mixed-effect models were used to predict velocity and stride length as a function of cue type and tempo (as fixed effects) and to account for the within-subject nature of the design (as random effects) using the lmer4 package in R. These models tested the main effects of Cue Type (Music v. Mental), Tempo (90, 100, 110, and 120%), and their interaction as categorical factors. Random effects of participant, the interaction of participant:cue type, and the interaction of participant:tempo were included to account for the within-subject nature of the manipulation. To determine the statistical significance of these effects, we used F-tests with Satterthwaite's approximation for the degrees of freedom. The Type I error rate for all tests was set at $\alpha=.017$ to account for multiple comparisons.

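### The mixed model omits the randomised Music/Mental position within each tempo, so an order effect costs precision and unequal carry-over stays hidden

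*Combined protocol and SAP*

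**What the plan says.** The Participants section describes the design: "As this was a within-group cross-over study, there was no control group and no group randomization". It also gives the size: "Seventeen individuals met these inclusion criteria and were enrolled in the study".

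The Protocol section sets the order of conditions: "To mitigate order effects, task order for each participant was randomized first by tempo", and the Music/Mental order was then randomised inside each tempo. As a result, "both cueing types at a given tempo occurred one after the other, but the order of cue type presented at each tempo was random". No counterbalancing is stated. No washout between cue types is described. Before every cued trial, "one chorus of the selected song was played at the correct tempo while the participant was standing still as a reminder of the tempo".

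The Statistical Analysis section gives the fixed part of the model for velocity and stride length: "These models tested the main effects of Cue Type (Music v. Mental), Tempo (90, 100, 110, and 120%), and their interaction as categorical factors". It gives the random part as follows: "Random effects of participant, the interaction of participant:cue type, and the interaction of participant:tempo were included". Tests are at alpha .017. No order, position, period or sequence term is listed, and no check for carry-over is described.

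**The concern.** The design treats order as something to guard against, but the analysis does not use it. Two consequences follow, and they differ in kind.

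- **Precision.** If walking changes from the first to the second cue type within a tempo (practice, fatigue, settling in), that change adds to or subtracts from each Music–Mental difference according to the random order. Without a position term it becomes residual noise. With 17 participants and a strict alpha, avoidable noise matters. It matters more for Cue Type × Tempo whenever participants differ in their cue effect: that variation cancels from the interaction contrast, so the order effect is a larger share of what remains.
- **Unequal carry-over.** Mental sometimes follows directly on three Music walks at the same tempo, and sometimes precedes them. If going second helps one cue type more than the other, the Music–Mental estimate is biased. Randomising the order does not remove this, and no planned output would reveal it.

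**Working it through.** **Inputs from the documents.** 17 participants; 4 tempos; 2 cue types; 3 trials per condition, averaged; alpha .017. The stated trial count reproduces: 3 uncued + 4 × 2 × 3 cued = 27. Participant-tempo pairs: 17 × 4 = 68. No SD, effect size or power is given, so every effect size below is an assumption.

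**Model for one pair.** D = Music − Mental = δ + d·s + u + e, where
- s = +1 if Music was second and −1 if it was first, at random;
- d = the second-minus-first shift;
- u = the participant's own cue effect;
- e = residual, with SD(e) = 1 setting the scale.

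**Cue Type, without a position term.** Var = SD(u)²/17 + 1/68 + d²/68. For SD(u) = 0.5 and d = 0 this is 0.25/17 + 1/68 = 0.0294, an SE of 0.17. Setting d = 0.25, 0.5 and 1.0 multiplies it by 1.031, 1.125 and 1.500.

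**Cue Type, with the term.** Generalised least squares, averaged over 4,000 random orders, multiplies the d = 0 variance by 1.015, 1.009 and 1.004 for SD(u) = 0, 0.5 and 1.0, whatever d is.

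Power below is for δ = 0.6, from the noncentral t on 16 df. The first figure in each of the last three columns is power without the term. The figure in brackets is the variance without the term divided by the variance with it.

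| SD(u) | Power with term | d = 0, no term | d = 0.25 | d = 0.5 | d = 1.0 |
|---|---|---|---|---|---|
| 0 | .98 | .982 | .975 (1.05) | .948 (1.23) | .787 (1.97) |
| 0.5 | .78 | .787 | .772 (1.02) | .730 (1.12) | .585 (1.49) |
| 1.0 | .35 | .356 | .351 (1.01) | .338 (1.05) | .293 (1.20) |

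**Cue Type × Tempo.** Here u cancels, so the error variance per pair is 1 + d² without the term and about 1.02 with it. The ratios are 1.04, 1.22 and 1.96. For tempo-specific differences of −0.67, −0.22, 0.22 and 0.67 around the mean cue effect, the noncentrality is 17 × (2 × 0.67² + 2 × 0.22²) = 16.9, divided by 1 + d². The noncentral F on 3 and 48 df gives power .84, .81, .73 and .46 for d = 0, 0.25, 0.5 and 1.0 without the term. With it, power is about .83 throughout.

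**Validity under a plain order effect.** Simulated bias was at most 0.004. Simulated type I error stayed between .015 and .019 against the nominal .017. The loss is therefore one of precision.

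**Chance imbalance.** Assuming simple randomisation, the mean of s over 68 pairs has SD 1/√68 = 0.12, so a typical trial carries about 0.12d in its Cue Type estimate. A 39:29 split or worse over all pairs has probability 27%. A 12:5 split or worse at a given tempo has probability 14%.

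**Unequal carry-over.** If Mental gains k only when second, then D = δ − k/2 + (k/2)s + u + e, a bias of −k/2. With SD(u) = 0.5 the variance is 0.0294 + (k/2)²/68. The probability of rejecting a true null of no cue difference rises from 1.7% to about 7%, 14% and 29% for k = 0.35, 0.5 and 0.71. In simulation, adding a position main effect left the bias unchanged.

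**The case against.** The strongest reply is that order was dealt with by design. Randomising separately within 68 pairs keeps the contrasts unbiased by a plain order effect and the tests valid, so the position term is an efficiency gain and does not rescue a faulty analysis. That stands.

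The large power losses also need a large order effect. At d = 1.0 the shift is 1.0/0.6 = 1.7 times the cue effect being tested. At d = 0.25 the loss is about one point of power, no more than the term itself costs when there is no order effect. That stands too, and the d = 1.0 figures should be read as an upper case. The greater loss for Cue Type × Tempo requires participants to differ in their cue effect. The plan itself includes that variance component, but its size is unknown.

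On carry-over, the chorus means that Mental follows same-tempo music in either order, which may shrink any inequality. However, the document presents the chorus as a tempo reminder, not a washout, and it does not address practice or fatigue.

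Finally, the carry-over checks are weak. For k = 0.5, comparing the first-of-pair estimate with the full estimate would detect the 0.25 shift at two-sided .05 only about 11% to 28% of the time; a Cue Type × position test would do so about 12% to 35% of the time. A null result would therefore reassure little. This argues for reporting an estimate with its interval and against using the check as a pre-test. It does not argue for leaving the issue unexamined.

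**Conclusion.** The concern holds. The omission is plain from the text; the size of its effect is not known. For a plain order effect the cost is power only: negligible at 0.25 pair-difference SD, up to about 6 points for Cue Type and 10 to 11 for Cue Type × Tempo at 0.5, and much more at 1.0. For unequal carry-over the cost is a bias of half the inequality, with no sign of it in the planned results. These figures rest on the assumed SDs and effects, on independent random order in each pair, and on complete data from all 17 participants. This is a recommended improvement to a valid analysis, held with medium confidence.

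**What to change.** - Add a fixed effect of within-tempo position (first/second) to both the velocity and the stride-length models.
- Position of the tempo block in the session (1–4) may be added as well. It bears on the Tempo comparison, not on Cue Type.
- As sensitivity checks only, report the Cue Type × position interaction with its interval, and the Music–Mental estimate from the first cue type in each tempo block. State that the latter is imprecise and may still carry over from the preceding block.
- Name unequal carry-over as a limitation, because the position term does not remove it.
- Label these terms post hoc if they are added after the data were analysed; the text is in the past tense.

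**Cost.** 1 df, or about 4 with block position. If there is no order effect, variance rises about 1% for Cue Type (at SD(u) = 0.5) and 2% for Cue Type × Tempo, and power falls from about 79% to 78% and from about 84% to 83%. The first-of-pair estimate has an SE of about 0.25 to 0.38, against 0.17 for the full contrast (participant:tempo SD assumed 0.25 to 1.0). All of this requires each participant's realised order to have been recorded, which the documents do not say.

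### Does the .017 threshold, which fits three tests, have to change because the plan describes six F-tests?

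*Combined protocol and SAP*

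**What the plan says.** Under Statistical Analysis, two outcomes are modelled: "Mixed-effect models were used to predict velocity and stride length as a function of cue type and tempo". The tests within each model follow: "These models tested the main effects of Cue Type (Music v. Mental), Tempo (90, 100, 110, and 120%), and their interaction as categorical factors". Inference is by F-test with Satterthwaite degrees of freedom. The section closes with one threshold: "The Type I error rate for all tests was set at" .017, "to account for multiple comparisons".

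The documents do not give the number of tests that the correction covers, the overall error rate it protects, a primary outcome or a primary effect. The Protocol section lists cadence beside velocity and stride length as a focus of the sensor recordings, but no model for cadence is described.

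The document reports finished work: "All data were analyzed using R statistical software".

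**The concern.** The number and the sentence around it seem not to match. A threshold of .017 is what a Bonferroni correction gives for three tests at 5%, but the sentence speaks of all tests and the section describes six. For six tests the Bonferroni value would be .0083. A reader who takes .017 as protection over everything tested would think the overall error is 5% when it could be nearly twice that.

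A conclusion could turn on this. Suppose the two Tempo tests have the smallest p-values and are rejected. A Cue Type p-value of .015 then counts as significant under the plan, but not under Holm over six tests, where the next step is .05/4 = .0125. Cue Type, the contrast of external with internal cueing, is central to the study, so the question is a fair one.

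**Working it through.** **Inputs from the documents.** Threshold .017; two outcomes; three effects per model; 17 participants, 2 cue types, 4 tempos. The correlation *r* between velocity and stride length is not given, so it is an assumption and is shown over its range.

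**Reproducing the plan's figure.** Bonferroni for three tests: .05/3 = .0167. Šidák for three tests: 1 − .95^(1/3) = .01695. Both round to .017. For two tests Bonferroni gives .025 and for six .0083, so neither fits. The divisor of three is inferred from this; the plan does not state it.

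**Three tests within one outcome.** In the balanced design, with random participant, participant-by-cue and participant-by-tempo terms, the tests have F(1,16) for Cue Type, F(3,48) for Tempo and F(3,48) for the interaction. Each uses its own error term. The chance of at least one false positive is 1 − (1 − .017)^3 = .0501, and the Bonferroni bound is 3 × .017 = .051.

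**Six tests pooled.** With independent outcomes it is 1 − (1 − .017)^6 = .0978, and the bound is 6 × .017 = .102.

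**If some Tempo effects are real.** A true effect cannot yield a false positive, so fewer tests count. With independent outcomes:
- one Tempo effect real, five nulls left: 1 − .983^5 = .082
- both real, four nulls left: 1 − .983^4 = .066

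**Correlated outcomes.** Simulation with the degrees of freedom above and the same *r* in every component (200,000 runs per value for six tests, 100,000 for four; Monte Carlo standard error below .001):

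| *r* (assumed) | Six tests, all nulls true | Four tests, both Tempo effects real |
|---|---|---|
| 0 | .097 | .067 |
| .5 | .094 | .064 |
| .7 | .089 | .059 |
| .9 | .076 | .050 |
| .95 | .069 | .046 |
| 1 | .051 | .035 |

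The simulation takes balanced data and exact F distributions. It does not cover singular fits or error in the Satterthwaite approximation.

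**What Holm over six would do.** Its steps are .0083, .01, .0125, .0167, .025 and .05. With all nulls true it holds the error at .049 (*r* = 0) to .034 (*r* = .95). A Cue Type test with 80% power at .017 (noncentrality 12.60) has 70% at the first step, 76% after two rejections and 80% after three. A Tempo or interaction test with 80% power at .017 (noncentrality 15.58) has 71.5% at the first step. Holm differs from the plan in both directions. Before any rejection, a p-value between .0083 and .017 passes the plan and fails Holm. After four rejections, a p-value between .017 and .025 fails the plan and passes Holm.

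**The case for a change.** The strongest case for a change is that the authors chose to correct for multiplicity, wrote that the threshold applies to all tests, and described six of them. On a plain reading the correction should then cover six, and at .017 it does not. The repair looks cheap, since Holm needs only p-values already computed and no new data or models.

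The arithmetic stands, and so does the remark that the family is not named. The inference to a wrong threshold does not. The sentence can equally mean that each test is judged at .017. It states no 5% rate across everything. Three effects per model is an ordinary family and matches the divisor. Three gait parameters is another possible source, given the mention of cadence. Whether to adjust across outcomes as well is a convention on which statisticians differ, and the documents make no commitment to it.

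The pooled figure of 7% to 10% also needs every null to be true, including no effect of Tempo on either outcome. Participants were told to walk to beats set between 90% and 120% of their own cadence, so that is not the obvious case.

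The repair is less cheap than it looks. The data had been analysed when the document was written, so changing the rule now would be a post hoc choice. Because Holm's later steps are looser than .017, the switch could even turn a result that failed the stated threshold into a significant one. A replacement family of exactly six would itself be a guess if cadence was also tested: three outcomes would make nine tests, with 1 − .983^9 = .143 under independence.

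**Conclusion.** No change to the plan follows. The threshold does what .05/3 is built to do: it holds error at about 5% over the three effects within each outcome. It does not hold 5% over all six tests, but the plan does not say that it does.

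The pooled excess depends on assumptions outside the documents. It is about 2 to 5 points if all six nulls are true and the outcome correlation lies between 0 and .95. If both Tempo effects are real it is at most about 1.7 points, and it vanishes at correlations of about .9 and above.

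Against that stand a loss of up to about 10 points of power at Holm's first step, a decision rule altered after the analysis, and a family that the documents do not establish. What is missing is a label for the family. A careful reader can infer it from the value itself, and supplying it would leave every test and threshold as they are. The per-outcome reading remains an inference, so the results should not be cited as controlling error at 5% across both outcomes together.

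### Holding every test at a fixed .017 is valid within a family of three but less efficient than Holm's step-down, which gives the same 5% guarantee; the power gain is conditional

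*Combined protocol and SAP*

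**What the plan says.** The multiplicity rule is one sentence at the end of Statistical Analysis: "The Type I error rate for all tests was set at" .017, with the stated purpose of allowing for multiple comparisons. No sequential step is described, no method is named, the overall error rate is not given, and the tests it is meant to cover are not listed.

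The same section describes the tests. "Mixed-effect models were used to predict velocity and stride length as a function of cue type and tempo", which makes two models. Within them, "These models tested the main effects of Cue Type (Music v. Mental), Tempo (90, 100, 110, and 120%), and their interaction as categorical factors", which makes three effects per model and 2 × 3 = 6 F-tests in all. The Protocol section also names three gait parameters, "with a focus on velocity, cadence, and stride length", a second possible origin for a divisor of three. The sample is 17 participants, all measured within subject (Participants section).

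**The concern.** A fixed threshold ignores what the other tests in the family show. Once one of three hypotheses has been rejected, a 5% family-wise guarantee can be kept with a more generous threshold for the remaining two. The plan does not use this.

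The design makes the point relevant. Cue tempos run from 90% to 120% of each participant's own cadence, and participants are asked to walk in time with the beat. If they do so, cadence changes, and velocity is cadence times step length. Tempo on velocity is then the likeliest rejection in its model. Yet Cue Type and Cue Type × Tempo, the two tests that compare music with mental singing, stay at .017 whatever Tempo shows. In a study of 17 people, power on those two tests is worth keeping where it costs nothing in guaranteed error control.

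**Working it through.** **Inputs from the documents.** Fixed threshold .017; three effects per model; two modelled outcomes; n = 17; F-tests with Satterthwaite degrees of freedom; random effects for participant, participant by cue type and participant by tempo.

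**Assumed, because the documents give no value.** Complete data, so degrees of freedom of about (1, 16) for Cue Type and (3, 48) for Tempo and for the interaction; independent test statistics for the power figures (Holm's error control does not need this); the family is the three effects within one outcome; standardised paired cue difference dz from 0.3 to 1.0.

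**1. The plan's figure.** Bonferroni: .05/3 = .01667, which rounds to .017. Sidak: 1 − .95^(1/3) = .01695, which also rounds to .017. Both are single-step rules. At .017 the bound for three tests is 3 × .017 = .051 (1 − .983³ = .0501 if independent).

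**2. Holm on the same three tests.** Order the p-values, compare them with .0167, .025 and .05 in turn, and stop at the first failure. Anything rejected at .05/3 is also rejected by Holm. The only exception against the printed rule is a smallest p-value between .0167 and .0170, which costs about 0.1 to 0.3 point of power.

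**3. Power of the Cue Type test at each threshold.** Noncentral t, 16 df, noncentrality dz × √17. For dz = 0.7 this is 0.7 × 4.123 = 2.886.

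| dz | at .017 | at .025 | at .05 | ceiling on gain (.05 minus .017) |
|---|---|---|---|---|
| 0.3 | 10.5% | 13.6% | 21.4% | 10.9 |
| 0.5 | 30.6% | 36.7% | 49.1% | 18.5 |
| 0.6 | 44.8% | 51.5% | 64.2% | 19.4 |
| 0.7 | 59.5% | 66.1% | 77.3% | 17.8 |
| 0.8 | 73.0% | 78.6% | 87.2% | 14.1 |
| 1.0 | 91.3% | 93.9% | 97.2% | 5.9 |

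**4. Holm power when Tempo is certain to be rejected.** Cue Type is then rejected if its p-value is at most .025, or at most .05 with the interaction p-value at most .025. Under independence:

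power = P(.025) + q × [P(.05) − P(.025)],

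where P(a) is the power of the cue test at threshold a, and q is the chance that the interaction p-value is at most .025.

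- dz 0.7, interaction null (q = .025): 66.1 + .025 × (77.3 − 66.1) = 66.4%, against 59.5% fixed. Gain about 7 points.
- dz 0.7, interaction with 50% power at .017 (q about .56): 66.1 + .56 × 11.2 = 72.4%. Gain about 13 points.

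Simulation with F(1,16), F(3,48) and F(3,48) tests and a Tempo noncentrality of 60 agrees: 59.6% fixed, 66.4% and 72.4% under Holm. For the interaction test at 50% power, Holm gives about 56% with no cue effect and 64% with dz 0.7.

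**5. How far the gain depends on the inputs (simulated, Cue Type, dz 0.3 to 1.0).**

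| Tempo | Interaction | gain in points |
|---|---|---|
| null | null | about 0 (−0.1) |
| 50% power | null | 1.3 to 3.4 |
| 80% power | null | 2.2 to 5.6 |
| certain | null | 2.7 to 7.1 |
| certain | 50% power | 4.5 to 13.9 |
| certain | 95% power | 5.8 to 18.9 |

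**6. Error control.** All three null: about 5.0% fixed and 4.9% Holm. Tempo real and the other two null: fixed 1 − .983² = 3.4%, Holm 1 − .975² = 4.9%. The same configuration in both outcomes, treated as independent: fixed 1 − .983⁴ = 6.6%, Holm within each outcome 1 − .975⁴ = 9.6%. The bound over six tests is 6 × .017 = 10.2% for the fixed rule and 2 × 5% = 10% for Holm within each outcome.

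**The case against.** The strongest reply is that a single-step .017 is a legitimate correction that nothing in the documents contradicts. That stands: this is lost efficiency, not invalid inference. It is still more than a matter of taste, because for any family of three Holm rejects at least as much (rounding apart) under the same guarantee.

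Second, the size of the gain depends on the family, which the plan never defines. If the divisor of three came from the three gait parameters, rejecting Tempo would free nothing for the cue tests. In such a family, Cue Type at dz 0.7 has 59.5% power fixed and 59.4% under Holm when the other two parameters show no cue effect, and gains 3 to 5 points when they carry dz 0.5. This stands. It limits the size of the gain, not its direction.

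Third, the fixed rule's slack is not wholly wasted. It keeps realised error over the two outcomes at 6.6% rather than 9.6% in the configuration above. A reader might infer that Holm costs nothing in error at study level. The guaranteed bound does stay at about 10%, but realised error moves towards it.

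Fourth, the argument that Tempo is nearly certain to be rejected concerns velocity only and assumes that participants follow the beat. Nothing comparable is shown for stride length.

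Finally, the document reports completed analyses in the past tense. Changing the rule now to one that in practice can only add rejections would be a post hoc relaxation. That stands and shapes the fix.

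**Conclusion.** The fixed .017 is consistent with a single-step Bonferroni or Sidak split of 5% over three tests. It is valid within one such family and less efficient than it need be. Holm on the same three tests keeps the 5% guarantee under any dependence.

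The gain is about 0 if no other test in the family is rejected. It is about 7 points for Cue Type with n = 17, dz 0.7 and Tempo on velocity in the same family and nearly certain to be rejected, and about 13 if the interaction also has 50% power. Over plausible inputs it runs from about 0 to 19 points.

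A reader might take a figure such as 6 to 14 points as a general property of this trial. The documents do not support that: they state no effect size, standard deviation or power, and do not place Tempo and Cue Type in one family. Nor do they support reading .017 as an error.

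**What to change.** In Statistical Analysis, first state which three tests form the family, for example Cue Type, Tempo and Cue Type × Tempo within each outcome. Then replace the fixed .017 with Holm's step-down within that family (.0167, .025, .05, stopping at the first failure) and report Holm-adjusted p-values. State that the 5% guarantee is per family and that the bound over both outcomes is about 10%.

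For data already analysed, keep the .017 result as planned and show the Holm result beside it, labelled post hoc. For analyses not yet run, or a later study, Holm can be prespecified.

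The cost is a few sentences and one call to `p.adjust` in R, with no new data and no change to the models. There are two downsides to state. Simultaneous confidence intervals matching Holm are less simple, though 98.3% intervals can still be shown. Realised error across the two outcomes can also rise towards its unchanged bound.
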